### 7.2. METHODS OF ANALYSIS

#### 7.2.1. Analysis of Marking in Peripheral Blood Mononuclear Cells

For OZ1 & LNL6 DNA-PCR (marking) the number and percentage of patients in each of the categories Not Detected, Detected (1/3 Detected, 2/3 Detected, 3/3 Detected) and Detected (Quantifiable). The number and percentage of patients in each category will be presented at each timepoint for 102/202 combined and overall for the PP population.

Patients who have quantifiable OZ1 & LNL6 DNA-PCR detected will have the value listed and the relationship between the % marking and calculated dose, age at infusion, gender and race explored as described below.

Correlation between OZ1 & LNL6 DNA-PCR (%) and calculated dose will be assessed using PROC CORR in SAS. The number of patients with quantifiable detected and calculated dose data, Spearman's rank correlation co-efficient and its associated p-value will be presented. Similar presentations will be made for OZ1 & LNL6 DNA-PCR (%) versus age and OZ1 & LNL6 DNA-PCR (%) and time since infusion (as defined in Section 6.3).

Association between the number of patients with and without OZ1 & LNL6 DNA-PCR quantifiable detection and gender will be assessed by the Chi-Squared test using PROC FREQ in SAS. The number of patients with data for both parameters, the Chi-Square statistic and its associated p-value will be presented. A p-value of less than 0.05 will indicate an association between the parameters. Similar presentations will be made for OZ1 & LNL6 DNA-PCR versus race and gender. If it is not appropriate to perform the Chi-Square test due to small cell sizes, Fishers Exact test will be performed.

<Protocol: Janssen OZ1-HV1-101/102/202>

<INC code: 1003733>

<SAP Version: 3.0>

---

The above analyses will be performed for 102/202 combined and overall at each post infusion timepoint for the PP population providing there are patients with quantifiable data to render the analyses meaningful. A review of the marker data will take place at the Data Review Meeting. All decisions taken regarding the above analyses will be fully documented in the meeting minutes.

The percentage of patients detected with either a quantifiable or non quantifiable OZ1 & LNL6 DNA-PCR result will be plotted over time for 101, 102 and 202 separately, 102/202 combined and overall for the PP population.

<Protocol: Janssen OZ1-HV1-101/102/202>

<INC code: 1003733>

<SAP Version: 3.0>

---

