### **3.2. STUDY SAMPLE SIZE**

The sample size of the long term follow-up studies is dependant on the number of patients continuing into the long term follow-up phase from the original studies. No formal sample size calculation was performed.

<Protocol: Janssen OZ1-HV1-101/102/202>

<INC code: 1003733>

<SAP Version: 3.0>

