3 years post infusion	Analysed Sample	n	
	Not Detected	n (%)	
	Etc...		

Note: Data summarized in this table are presented in data listing x.x

\* = OZ1 & LNL6 DNA Detected but below the lower quantitative limit of the assay: 1/3 = 1 of the 3 triplicates of the sample were detected; 2/3 = 2 of the 3 triplicates of the sample were detected; 3/3 = 3 of the 3 triplicates of the sample were detected.

DDMMYYYY HH:MM

*Prgm note: % based on N*

*Programming note: Please repeat this table for 14.2.1.1a (Study 202 only)*

<Protocol: Janssen OZ1-HV1-101/102/202>

<INC code: 1003733>

<SAP Version: 3.0>

Janssen - OZ1-HVI-101/102/202

TABLE 14.2.1.2

Page x of y

OZ1 and LNL6 DNA PCR  
Relationship Between Marking Parameters (PBMC) and Calculated Dose, Age, Time on Study, Gender and Race  
Summary Statistics: PP Population

Visit	PBMC versus	Statistic	OZ1-HV1-102 / OZ1-HV1-202 (N = XX)	Overall (N = XX)
2 years post infusion	Calculated Dose	N (1) Rho (2) p-value		
	Age (3)	N (1) Rho (2) p-value		
	Time on Study	N (1) Rho (2) p-value		
	Gender	N (1) Chi-Square (4) p-value		
	Race (5)	N (1) Chi-Square (4) p-value		
2.5 years post infusion Etc..	Calculated Dose	N (1) Rho (2) Etc..		

Note: Data summarized in this table are presented in data listing x.x  
 (1) N = number of patients with quantifiable OZ1 & LNL6 DNA detected  
 (2) Rho = Spearman's Rank Correlation co-efficient  
 (3) = Age at infusion

<Protocol: Janssen OZ1-HV1-101/102/202>

<INC code: 1003733>

<SAP Version: 3.0>

---

(4) = Chi-Square statistic

(5) = Race categories (Aboriginal, African American, American Indian, Asian, Caucasian, Hispanic, Maori/Polynesian, Other  
DDMMYYYY HH:MM

*Prgm note: Fishers Exact test may be presented if Chi-Square test is not appropriate*

*Programming note: Please repeat this table for 14.2.1.2a (Study 202 only)*

<Protocol: Janssen OZ1-HV1-101/102/202>

<INC code: 1003733>

<SAP Version: 3.0>

Janssen - OZ1-HVI-101/102/202

TABLE 14.3.1

Page 1 of x

Overall Summary of Adverse Events  
Summary Statistics: Safety Population

	OZ1-HV1-101 (N=xx)	OZ1-HV1-102 (N=xx)	OZ1-HV1-202 (N=xx)	Overall (N=xx)
Number (%) of patients with at least one SAE				
Number (%) of patients with at least one related SAE				
Number (%) of patients with at least one severe related SAE				
Number (%) of patients with least one NSRAE				
Number (%) of patients with SAE/NSRAE leading to death				
Number of SAEs				
Number of related SAEs				
Number of severe related SAEs				
Number of NSRAEs				

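### Spearman p-values for marking come from PROC CORR with no minimum n and no exact method, so they would be materially wrong at any visit with only 3 to 5 quantifiable patients

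*SAP*

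**What the plan says.** SAP 7.2.1 relates the percentage of marked cells to calculated dose: "Correlation between OZ1 & LNL6 DNA-PCR (%) and calculated dose will be assessed using PROC CORR in SAS". It adds that "Spearman's rank correlation co-efficient and its associated p-value will be presented", and asks for the same against age and time since infusion. Only patients with a quantifiable result contribute; the shell for Table 14.2.1.2 defines "N = number of patients with quantifiable OZ1 & LNL6 DNA detected".

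The analysis is repeated by visit: "The above analyses will be performed for 102/202 combined and overall at each post infusion timepoint for the PP population". Table 14.2.1.2a repeats it for study 202 alone.

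The section makes three provisions for sparse data:
- The analyses run only "providing there are patients with quantifiable data to render the analyses meaningful".
- The marker data go to the Data Review Meeting, whose decisions on these analyses are minuted.
- For the categorical tests, "If it is not appropriate to perform the Chi-Square test due to small cell sizes, Fishers Exact test will be performed".

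No number is attached to the first two, and the third does not extend to the correlations. A significance rule, "A p-value of less than 0.05 will indicate an association between the parameters", stands in the chi-square paragraph; none is stated for Spearman. On numbers, SAP 3.2 says "No formal sample size calculation was performed". SAP 8.2.5 also takes a Spearman p-value from PROC CORR, for serious and non-serious related adverse events.

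**The concern.** The t approximation for a rank correlation breaks down when n is very small. With perfect agreement of ranks the t statistic is infinite, so the p-value prints as essentially zero whether n is 3 or 30. The visits with least data could then show the most striking p-values.

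The plan protects the chi-square tests, which compare patients with and without a quantifiable result. It does not protect the correlations, which use the quantifiable patients only and so have the smaller n. Marking over time is a stated objective (SAP 2), and a dose correlation printed as <.0001 from three or four patients could be quoted as a dose-response finding. This is an error within each single test and is separate from the number of tests.

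**Working it through.** The documents give no sample size, power or p-value for this analysis, so there is no figure of theirs to reproduce.

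**Inputs**
- Procedure and statistic: PROC CORR, Spearman rho with its p-value (SAP 7.2.1).
- n: patients quantifiable at that visit (shell for Table 14.2.1.2). The count is not given, so n = 3 to 9 is examined as an assumed range.
- Assumptions: two-sided p-values, no ties, PROC CORR's default t approximation, and very small p-values printed as <.0001. The last two are knowledge of the software, not statements in the SAP.

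**Formulas**
- Approximate p: t = rho × sqrt((n − 2)/(1 − rho²)), referred to a t distribution on n − 2 degrees of freedom.
- Exact p: the share of all n! orderings with |rho| at least as large as observed. For a perfect ordering, up or down, this is 2/n!.

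**Perfect ordering.** With rho = ±1, 1 − rho² = 0, so t is infinite and the approximate p is 0 at every n. The exact p is 2/6 = 0.333 at n=3, 2/24 = 0.083 at n=4 and 2/120 = 0.017 at n=5.

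**Near-perfect orderings**
- n=5, rho=0.9: t = 0.9 × sqrt(3/0.19) = 3.58 on 3 df, approximate p = 0.037. Exactly, 10 of 120 orderings are as extreme, p = 0.083.
- n=6, rho=0.829: t = 0.829 × sqrt(4/0.3135) = 2.96 on 4 df, approximate p = 0.042. Exactly, 42 of 720, p = 0.058.

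**Behaviour under no association, by full enumeration**

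| n | P(approx. p<0.05) | P(approx. p<0.0001) | Exact p, perfect ordering | Size of exact test at 0.05 |
|---|---|---|---|---|
| 3 | 33.3% | 33.3% | 0.333 | 0% |
| 4 | 8.3% | 8.3% | 0.083 | 0% |
| 5 | 8.3% | 1.7% | 0.017 | 1.7% |
| 6 | 5.8% | 0.28% | 0.0028 | 3.3% |
| 7 | 4.8% | 0.04% | 0.0004 | 4.8% |
| 8 | 5.8% | 0.04% | 0.00005 | 4.6% |
| 9 | 5.9% | 0.04% | 0.000006 | 4.3% |

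At n=3 and n=4 no ordering can reach an exact p below 0.05, so every result the approximation calls significant is one that the exact test could not. At n=5 the excess comes from the rho = ±0.9 orderings; a perfect ordering is below 0.05 either way. From about n=7 the size at 0.05 is close to nominal, although p-values further into the tail are still too small (n=7, rho=0.964: 0.00045 against 0.0028).

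**The case against.** The strongest reply is that the problem is conditional and the stakes are low. Several stronger readings are tempting, and the documents do not support them.

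- **That the SAP expects only a handful of quantifiable patients.** It does not say so. The proviso and the Fisher fallback show that sparse data were allowed for. No per-visit count appears anywhere. Protocol 1.1 implies about 37 OZ1 recipients in the parent trial (half of 74), before attrition and before requiring a quantifiable result. That neither establishes nor excludes n of 3 to 5.
- **That the table will print wrong p-values.** The proviso and the Data Review Meeting are a partial gate aimed at just this case, and may remove the smallest visits. What stands is that the gate has no numerical criterion and operates after the marker data have been seen.
- **That chance results at <.0001 are a general hazard.** Their probability falls from 33.3% at n=3 to 8.3%, 1.7% and 0.28% at n=4, 5 and 6. The gross error is confined to n=3 and n=4.
- **That false associations would be declared.** SAP 7.2.1 calls these relationships explored, Protocol 9 makes the main analysis descriptive, no decision depends on the p-values, and the 0.05 rule is not written for Spearman. The shell prints N and rho beside each p-value, so a careful reader would see N=3 and rho=1.

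These replies limit the size of the point. They do not supply an exact method or a minimum n, which the section lacks for the correlations although it provides an exact test for the categorical comparisons.

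**Conclusion.** The point holds as a conditional, minor one. If PROC CORR's default t approximation is used and a visit has 3 to 5 quantifiable patients without ties, the Spearman p-values are materially wrong. The false-positive rate at 0.05 is 33%, 8.3% and 8.3% at n=3, 4 and 5, and a perfect ordering prints as <.0001 against exact values of 0.33, 0.083 and 0.017. At n=6 the effect is slight, and from about n=7 the size at 0.05 is near nominal. Whether any visit falls in the affected range cannot be told from the documents. Severity is minor because the analysis is exploratory and N and rho are shown, but the correction is cheap enough to make.

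**What to change.** In SAP 7.2.1, specify the two-sided exact permutation p-value for Spearman (PROC FREQ with EXACT SCORR), with a Monte Carlo estimate where full enumeration is impractical. State that when n is 4 or less only rho and N are printed, since no ordering can then reach p<0.05. This also gives the Data Review Meeting a numerical rule fixed in advance. Add a footnote to the shells for Tables 14.2.1.2 and 14.2.1.2a.

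Apply the same rule to SAP 8.2.5 and Table 14.3.5. There the text gives one p-value across timepoints while the shell shows rho and p at each visit, so the rule should cover whichever layout is kept.

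The cost is a small change to programming, shells and validation, because the p-value comes from a different procedure. Some p-values will become less favourable. At visits with about seven or more quantifiable patients, conclusions at 0.05 should change little.

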## 5. OVERALL CONSIDERATIONS

All summary tables and data listings produced by INC will use the statistical package SAS (v9.2 or a more recent version).

In general, categorical data will be presented using counts and percentages, whilst continuous data will be presented using the descriptive statistics, mean, standard deviation (SD), median, minimum, maximum and number of patients with an observation (n). Minimum and maximum values will be quoted to the number of decimal places as recorded on the CRF; means, medians and SDs will be quoted to one further decimal place. Percentages will be rounded to one decimal place. Percentages smaller than 0.1 will be presented as <0.1. Percentages whose numerator is zero will be reported as zero.

All data recorded on the Case Report Form (CRF) and any derived data will be listed for all patients.

The Safety population will be used to present Adverse Event and death data. The PP population will be used to present all data .

Unless otherwise stated missing data will not be imputed. Patients who withdraw prematurely will have their data summarized at the last attended visit. Repeat assessments will not be summarized unless otherwise indicated but will be fully listed. Similarly, data collected at unscheduled visits will be listed only. Repeat and unscheduled visits will be identified on the data listings.

Where of interest, presentation of data will be pooled to reflect the target cell type, CD4 cells in OZ1-HV1-101 and CD34 cells in OZ1-HV1-102 and OZ1-HV1-202 in addition to presenting separately and overall.

<Protocol: Janssen OZ1-HV1-101/102/202>

<INC code: 1003733>

<SAP Version: 3.0>

---

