## 7. EFFICACY

### 7.1. MARKING IN PERIPHERAL BLOOD MONONUCLEAR CELLS

PBMC analysis (OZ1 & LNL6 DNA PCR (marking)) will be performed at 2 years post infusion or the nearest timepoint before starting the long term follow-up and at each 6 monthly visit up to 5 years post infusion and annually there after. Analyzed samples for gene detection will be classified as either not done, not detected or detected. If detected genes are found these will further be classified as to whether they are below the limit of quantification or not. Samples below the limit of quantification will be classified as either 1/3 (genes detected in 1 of the 3 triplicates of the sample), 2/3 (genes detected in 2 of the 3 triplicates of the sample) or 3/3 (genes detected in 3 of the 3 triplicates of the sample). For samples above the limit of quantification the percentage detected will be recorded for OZ1 & LNL6 DNA-PCR.

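### The marking correlations use only patients with quantifiable marking, which selects on the outcome; an all-patient rank correlation should be shown beside them

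*SAP*

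**What the plan says.** SAP 7.1 sorts each analysed sample into an ordered set of results. A sample is either not detected or detected. If it is detected but not quantifiable, it is graded by how many of its three replicates were positive: "Samples below the limit of quantification will be classified as either 1/3", and likewise 2/3 or 3/3. A percentage exists only at the top of the scale: "For samples above the limit of quantification the percentage detected will be recorded for OZ1 & LNL6 DNA-PCR".

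SAP 7.2.1 then limits the exploration of factors to that top group: "Patients who have quantifiable OZ1 & LNL6 DNA-PCR detected will have the value listed and the relationship between the % marking and calculated dose", followed by age, gender and race. For dose the method is rank correlation: "Spearman's rank correlation co-efficient and its associated p-value will be presented". The count reported with it is "The number of patients with quantifiable detected and calculated dose data". The same presentation is planned for age and for time since infusion. Footnote (1) of the Table 14.2.1.2 shell confirms the restriction: "N = number of patients with quantifiable OZ1 & LNL6 DNA detected". SAP 5 adds that "Unless otherwise stated missing data will not be imputed", so nothing puts a value or rank on the excluded results.

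Gender and race are handled differently. The planned test is of "Association between the number of patients with and without OZ1 & LNL6 DNA-PCR quantifiable detection and gender", which keeps the non-quantifiable patients, with a similar presentation for race.

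**The concern.** The question is whether dose, age or time predicts marking, yet a patient enters only if marking was high enough to quantify. Low responders are removed together with their doses. Under a simple increasing dose-response this does two things: it narrows the range of marking, which weakens the correlation, and it reduces the number of patients.

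No other planned analysis relates dose to marking. None compares dose between quantifiable and non-quantifiable patients, and no sensitivity analysis brings the excluded patients back. A small, non-significant rho could therefore be read as showing that dose does not matter, when the low end of the response had been removed by design.

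The restriction is also avoidable. Spearman's rho needs only an order, and SAP 7.1 already records one.

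**Working it through.** **No stated figure to reproduce.** The documents give no power, expected correlation, limit of quantification or expected share of quantifiable samples. SAP 3.2 says that no formal sample size calculation was done. The size can only be illustrated.

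**Inputs**
- N = 37: half of the 74 patients in Protocol 1.1 (74 / 2 = 37). This scales the study 202 table (14.2.1.2a) and is not a count of samples at any visit.
- True Spearman correlation 0.5: assumption.
- Quantifiable share 25%, 50% or 75%: assumption. That is about 9, 18 or 28 of 37 patients (37 × 0.25 = 9.25; 37 × 0.50 = 18.5; 37 × 0.75 = 27.75).
- Two-sided 0.05: SAP 7.2.1 states this threshold for the Chi-Square test; using it for Spearman is an assumption.

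**Model A: results are non-quantifiable because marking is low.** Dose and latent marking are bivariate normal on a monotone scale. The link between latent correlation r and Spearman is rho_S = (6/π) × arcsin(r/2). For example, r = 0.5 gives (6/π) × arcsin(0.25) = 0.48. The highest-marking patients are quantifiable. In the category ranking, half of the others are not detected and half are split equally over 1/3, 2/3 and 3/3.

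| Quantifiable | Plan: mean rho | Plan: p<0.05 | All patients, non-quantifiable tied lowest: mean rho | All patients, ranked by category: mean rho | Ranked by category: p<0.05 |
|---|---|---|---|---|---|
| 25% | 0.23 | 11% | 0.37 | 0.46 | 85% |
| 50% | 0.30 | 25% | 0.45 | 0.48 | 87% |
| 75% | 0.38 | 53% | 0.48 | 0.48 | 89% |

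With no true relation, both the planned rule and the category ranking give p<0.05 in about 5% of runs.

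**Is this only a small-sample effect?** No. With 400,000 simulated patients and r = 0.5 (full-data rho 0.484), the planned rule gives 0.247, 0.309 and 0.372 at 25%, 50% and 75% quantifiable. As shares of the full value these are 0.247/0.484 = 0.51, 0.309/0.484 = 0.64 and 0.372/0.484 = 0.77. Over r = 0.3, 0.5 and 0.7, and 10% to 75% quantifiable, the planned rho is 37% to 82% of the full value.

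**Model B: non-quantifiable status is unrelated to dose**, for instance engraftment failure at random. With N = 37 and true Spearman 0.5 among those who mark, the planned rho stays at about 0.47. The all-patient rho falls to 0.03, 0.11 and 0.28 at 25%, 50% and 75% quantifiable.

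**Model C: the spread of marking rises strongly with dose.** In one simulated case the full-data rho was 0.23 and the planned rule gave 0.46 to 0.49, so the restriction can also inflate.

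**Calculated dose.** SAP 6.4 divides dose by 100 and multiplies by transduction efficiency. The Table 14.1.5 footnote divides dose by the product of 100 and transduction efficiency. Take two patients with equal dose 10 and efficiencies 20 and 40 (invented values). SAP 6.4 gives 10/100 × 20 = 2 and 10/100 × 40 = 4. The footnote gives 10/(100 × 20) = 0.005 and 10/(100 × 40) = 0.0025. The order reverses, so a rank correlation depends on which formula is programmed.

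**Footnote (1) against the text.** The footnote is attached to N in every row of Table 14.2.1.2, including gender and race. Read literally, those rows would contain only quantifiable patients and leave no second group to compare. SAP 7.2.1 instead counts patients who have data for both parameters.

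**The case against.** A reader might infer that the planned dose-response is biased towards zero as a matter of fact, and that ranking everyone restores it. The documents do not support that. They do not say why a sample falls below the limit. Under Model B the planned rho is the undistorted one among patients who mark, and the all-patient rho answers a different question, mixing whether marking is present with how high it is. This part of the objection stands, and it is why both correlations are needed.

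The gain is also a best case. The 85% to 89% assumes that replicate counts order below-limit samples without error, and SAP 7.1 gives no information on that. With 25% quantifiable and uninformative categories, the all-patient rho is about 0.29 with p<0.05 in 43% of runs. That is still above the plan's 0.23 and 11%, but far from 85%. If the true Spearman correlation is 0.3, even the category ranking reaches only about 38% to 43%.

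The consequence is limited. Protocol 9 calls the analysis primarily descriptive and says that associated factors may be assessed; no decision hangs on rho. The category table covers all patients, marking and treatment details are listed for all, and the Data Review Meeting reviews the marker data. These soften the point without answering it: none of them relates dose to marking in the excluded patients, and the meeting is not asked to consider the restriction.

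**Conclusion.** The restriction is explicit in the SAP text and in the table shell, it selects on the outcome, and nothing else in the plan offsets it. Attenuation is the expected result if low marking is what makes a sample non-quantifiable and marking rises with dose. Under those assumptions the planned rho is about 0.23 to 0.38, against 0.37 to 0.48 with all tested patients kept. Under other plausible mechanisms the planned rho is intact or even too high. The direction is therefore conditional, and the size cannot be fixed from the documents.

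What does not depend on the mechanism is that the quantifiable-only rho, shown alone, cannot tell these cases apart. This is a worthwhile and cheap improvement to an exploratory analysis; it does not invalidate the plan. The footnote mismatch in the gender and race rows and the two dose formulas are separate inconsistencies in the same output. They need correcting whatever view is taken of the bias.

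**What to change.** 1. In SAP 7.2.1 and Tables 14.2.1.2 and 14.2.1.2a, run the Spearman correlations with calculated dose, age and time since infusion (the row labelled time on study) on all per-protocol patients with an analysed sample at the visit. Rank marking as not detected < 1/3 < 2/3 < 3/3 < quantifiable percentage, with ties averaged.
2. As a check, repeat with all non-quantifiable results tied at the lowest rank.
3. Report the quantifiable-only rho beside it, with its own N, and say that the two answer different questions.
4. Change footnote (1) so that N is patients with an analysed sample and a non-missing factor. The gender and race rows then agree with the text.
5. Reconcile the calculated-dose formulas in SAP 6.4 and the Table 14.1.5 footnote before any dose correlation is run.

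The cost is SAP wording, one derived rank variable and extra rows in two tables, with no new data. The downsides are that the order of the replicate categories may be noisy, and that the all-patient rho combines presence of marking with its level.

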9. STATISTICAL METHODS[†]

Statistical analysis of data collected during the long term follow-up study will be performed every 5 years. After patients complete an End-of Study visit, the final analysis of data will be done. The primary focus of analysis will be descriptive summarizing changes over time. Patterns over time will be analysed using appropriate techniques. Factors associated with quantitative changes may be assessed.

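### SAP 7.2.1 declares an association whenever a gender or race test of quantifiable marking gives p<0.05, and repeats those tests visit by visit with no adjustment or nominal label

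*SAP*

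**What the plan says.** SAP 7.2.1 describes two kinds of test.

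- **Calculated dose, age and time since infusion** are related to percentage marking by rank correlation: "Spearman's rank correlation co-efficient and its associated p-value will be presented". That paragraph sets no threshold.
- **Gender** is related to whether marking is quantifiable (yes or no) by chi-square, with Fisher's exact test as the fallback for small cells. The decision rule stands in this paragraph: "A p-value of less than 0.05 will indicate an association between the parameters". The next sentence extends the approach to race: "Similar presentations will be made for OZ1 & LNL6 DNA-PCR versus race and gender".

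The section then sets the repetition, "The above analyses will be performed for 102/202 combined and overall at each post infusion timepoint for the PP population", subject to a condition, "providing there are patients with quantifiable data to render the analyses meaningful". Marker data are reviewed at the Data Review Meeting, where decisions on these analyses are minuted.

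The shell of Table 14.2.1.2, titled "Relationship Between Marking Parameters (PBMC) and Calculated Dose, Age, Time on Study, Gender and Race", prints a p-value for each of the five factors at each visit. A programming note repeats the whole table for study 202 as Table 14.2.1.2a.

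Protocol section 9 sets the general tone: "The primary focus of analysis will be descriptive summarizing changes over time". It also allows that factors associated with quantitative changes may be assessed.

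**The concern.** The 0.05 sentence is a rule for drawing a conclusion, not a description of output. Applied as written, it makes one gender or race p-value below 0.05, at one visit in one column, a reported association. The rule is applied many times to the same patients, and nothing in either document limits the error over the set: no adjustment, no primary timepoint, no statement that the p-values are nominal.

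Quantitative marking is the third study objective and the only efficacy evaluation. The risk is that the final report states a demographic association with persistence of the gene transfer product that is a chance result. Visits share patients, and study 202 lies inside 102/202, which lies inside the overall column. One chance imbalance can therefore show up at several visits and in up to three columns, where a reader may take it for confirmation.

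**Working it through.** The plan gives no number of tests, error rate, sample size or power for these analyses, so there is no figure to reproduce.

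**Timepoints.** SAP 7.1 and the Table 14.2.1.2 shell give years 2, 2.5, 3, 3.5, 4, 4.5 and 5, which is 7, and then annual visits. SAP Table 2 requires at least 10 years of follow-up in study 202, adding years 6 to 10: 7 + 5 = 12. SAP Table 1 schedules the PCR to year 15, which would give 17, though few patients would contribute late.

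**Factors under the rule.** Two: gender explicitly, race by extension.

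**Columns.** Two in Table 14.2.1.2, and a third in Table 14.2.1.2a.

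**Formulas.** Tests per column m = timepoints × 2. Expected false positives = 0.05 × m, which does not depend on correlation between tests. Chance of at least one, if independent = 1 − 0.95^m.

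| Through | Timepoints | Tests per column | Expected false positives | At least one, if independent |
|---|---|---|---|---|
| Year 5 | 7 | 14 | 0.70 | 51% |
| Year 10 | 12 | 24 | 1.20 | 71% |
| Year 15 | 17 | 34 | 1.70 | 83% |

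For gender alone through year 10: 12 tests, 0.6 expected, 46% if independent.

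**Effect of shared patients.** Two null factors were simulated over 12 visits in two nested columns (48 tests). The inputs were assumed: 47 and 51 patients, with rank correlation standing in for the categorical tests. The mean number of false positives stayed near 48 × 0.05 = 2.4. The chance of at least one was 79%, 65%, 43% and 26% at between-visit correlations of 0, 0.5, 0.8 and 0.95, against 91% under full independence. Fewer runs of the study produce a false positive, but those that do produce several.

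**Effect of Fisher's test.** Take 47 patients: about half of the 74 in the Phase II trial is 37, plus an assumed 10 from study 102. Assume also 30% quantifiable and 4 or 8 patients in the smaller gender group. The exact size of Fisher's test is then 0.0177 or 0.0302.

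- Gender, 12 visits: 12 × 0.0177 = 0.21, or 12 × 0.0302 = 0.36 expected per column.
- In simulation, with an assumed between-visit correlation of 0.3 to 0.9 on an underlying normal scale, the chance of at least one false gender result per column was about 8% to 29%.
- Adding race at its nominal 12 × 0.05 = 0.60 gives 0.81 to 0.96 per column, against 1.20 at the nominal level throughout.

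The documents do not give the gender split, the share quantifiable or the patient numbers by column.

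**The case against.** The strongest case on the other side is that these analyses are exploratory and the plan presents them so. The SAP speaks of exploring the relationships, and no sample size was calculated. Tests run only where the data make them meaningful, and the protocol expressly permits assessment of associated factors. The table shows every visit and factor together, so an isolated result can be seen as isolated. Fisher's test is conservative in small cells.

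Most of this stands, and it limits the size of the point. It does not remove it. The rule still says what a p-value below 0.05 means, and the general word about exploration does not cancel it. The condition on meaningful data has no stated criterion; it can reduce the number of tests but controls no error rate.

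A reader might go further, in three ways that the documents do not support:

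- **That the rule covers all five factors.** This would give 12 × 5 = 60 tests and 3.0 expected false positives per column. The rank-correlation paragraph only presents its p-values, so no conclusion about dose, age or time is forced.
- **That the columns add up to separate evidence.** Three columns of gender and race tests make 72 tests and 3.6 expected false positives. The sum is correct as a count, but largely the same patients are being counted up to three times.
- **That the independence percentages are the real risk.** They assume unrelated visits, whereas the same patients are tested each time.

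**Conclusion.** The point holds for the gender and race tests. SAP 7.2.1 attaches a conclusion to each unadjusted p-value below 0.05 and repeats the tests at every timepoint with meaningful data. Through year 10 that is up to 24 tests per column and at most about 1.2 expected false positives at a nominal 5%. Under the assumptions above it is nearer 0.8 to 1.0 if Fisher's test is used for gender. The chance of at least one per column lies below 71%; how far below depends on the between-visit correlation and the cell sizes, which the documents do not give. Because columns and visits overlap, apparent repetition of a result is weak evidence that it is real.

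The consequence is confined to exploratory marking analyses. No primary endpoint or safety conclusion depends on these tests. The sentence should still be changed, because following it can turn a chance result into a stated finding and removing it costs very little.

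**What to change.** 1. Delete the 0.05 sentence from SAP 7.2.1.
2. State there, and in footnotes to Tables 14.2.1.2 and 14.2.1.2a, that all by-visit p-values are nominal and exploratory, that no association is concluded from a single visit, and that consistency across visits will be described, bearing in mind that visits and columns share patients.
3. Show the rank correlation with a 95% confidence interval for dose, age and time, and the difference in proportion quantifiable with a 95% confidence interval for gender.
4. If one overall test per factor is wanted for gender and race, base it on a per-patient binary summary, such as ever quantifiable, or on a repeated-measures model for the binary outcome. Mean log marking would not serve: these tests concern quantifiable yes or no, and a percentage is recorded only above the limit of quantification. An ever-quantifiable summary also depends on how many samples a patient gave, so the number tested should be shown beside it.

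Steps 1 and 2 need wording only, and step 3 a small change to the table programs. Step 4 is optional and needs a short extra program. No new data are required. The price is that no association can be claimed from an isolated visit.
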